6.3.2 Follow-up for toxicities

Refer to [Table 6-2](#), [Table 6-3](#) and [Section 6.3.3](#).

6.3.3 Anticipated risks and safety concerns of the study drug

Appropriate eligibility criteria, specific dose modification and stopping rules are included in this protocol. Recommended guidelines for prophylactic or supportive treatment for expected toxicities, including management of study-drug induced adverse events, i.e., hyperglycemia, QT prolongation and LFT abnormal are provided below. Refer to preclinical toxicity and or clinical data found in the [Investigator's Brochure].

6.3.3.1 Hyperglycemia

Hyperglycemia is known to be associated with the treatment of somatostatin analogues (SSA). Clinical studies of pasireotide in healthy volunteers and in patients with Cushing's disease, acromegaly or carcinoid syndrome have reported transient, asymptomatic increases in fasting and postprandial glucose levels. Two clinical studies have been conducted ([SOM230B2216] and [SOM230B2124]) in healthy volunteers to further understand the mechanism of pasireotide-induced hyperglycemia and to evaluate the potential clinical utility of anti-diabetes agents in the management of pasireotide-induced hyperglycemia. Data from ([SOM230B2216] study indicate that pasireotide decreases insulin secretion, particularly in the postprandial period, as well as the GLP-1/GIP secretion. Results from [SOM230B2124] study suggest that the incretin-based therapies (GLP-1 analogues and DPP-4 inhibitors) may have the best potential to manage the hyperglycemia associated with pasireotide.

Monitoring of blood glucose

Close and frequent monitoring of blood glucose is needed during pasireotide treatment. The principal investigator is to educate the patient on the signs and symptoms of hyperglycemia. Patients must monitor their fasting blood glucose by fingerstick at home at least 3 times per week for the first month of pasireotide LAR treatment. If a patient does NOT have any fasting values above 100 mg/dL, monitoring can be decreased to at least 2 times per week for months 2 and 3 and 1 time every 2 weeks for 4 months through 6 months. If glucose values remain normal (lower than or equal to 100 mg/dL), monitoring is at the investigator's discretion after 6 months. If any values are observed above 100 mg/dL, the guidelines in [Figure 6-1](#) are to be followed. These guidelines are based on the current recommendations from the 2012 American Diabetes Association and European Association for the Study of Diabetes aiming at a glycemic treatment goal of FPG <130 mg/dL (<7.2 mmol/L). Appropriate actions such as initiation of anti-hyperglycemic therapy (and referral to diabetes specialist) are to be taken by the investigator as outlined on [Figure 6-1](#). If fasting blood glucose values dictate initiation of anti-hyperglycemic treatment (i.e., confirmed >130 mg/dL by self-monitoring), a fasting plasma glucose sample using the local laboratory is to be collected prior to initiation of anti-hyperglycemic treatment. If a patient has a dose increase, monitoring for hyperglycemia should follow the recommendations for the first month of treatment and continue as presented above for subsequent months.

[figure not shown]
It is recommended that the patients be encouraged to keep a diary for their blood glucose for appropriate management throughout the study and present the collected data to their physician/diabetes specialist for evaluation. This data will not be collected by the sponsor.

In addition to self-monitoring, fasting plasma glucose and HbA1c will be collected at study visits per [Table 7-1](#) and [Table 7-2](#). Intervention for hyperglycemia is to be implemented in any patient meeting any of the following criteria: FPG > 130 mg/dL or HbA1c ≥ 6.5 %.

Patients with FPG > 160 mg/dL or HbA1c >7.5% despite adjustment of antidiabetic therapy should be referred to a diabetes specialist (or earlier per investigator’s judgment).

As outlined in [Table 6-2](#), patients with grade 3 hyperglycemia (FPG value >250 mg/dL; >13.9 mmol/L) at any point in the study should have the dose of pasireotide decreased. Patients who in spite of appropriate therapeutic interventions and despite dose reduction of study drug develop uncontrolled diabetes mellitus and/or consistently high blood glucose values: FPG ≥ 240 mg/dL (13.3 mmol/L) or HbA1c value ≥ 10 % will require study treatment discontinuation as outlined in [Section 7.1.3.1](#).

Figure 6-1 Fasting self-monitoring blood glucose guidelines

6.3.3.2 QT-related cardiology consultation / Holter monitoring

All patients will be asked to return on Day 22 for an ECG recording and PK sampling.

If at any visit a QTcF > 500 msec is observed, triplicate ECGs, each 2-3 minutes apart, need to be taken approximately 1 hour after the initial ECG. The mean QTcF from the triplicate ECGs will be determined. If the mean QTcF is > 500 msec, the patient has to postpone study treatment until a cardiologist has re-evaluated the ECG (this can be done by the central cardiologist). The re-evaluation needs to be done as soon as practical but within 7 days of the

initial abnormal ECG. If the cardiologist confirms a mean QTcF > 500 msec, the patient must be discontinued from the study. Otherwise and if the cardiologist confirms that at least one ECG shows a QTcF > 470msec, the cardiac assessments described for a confirmed QTcF > 470 msec needs to be followed.

If at Day 22 a QTcF / mean QTcF > 470 msec but \leq 500 msec is observed for the first time for a patient at a given dose level, the following steps need to be taken (please also refer to [Figure 6-2](#)):

A cardiology consultation must be sought as soon as practical but within 7 days of the initial abnormal ECG and prior to the next pasireotide LAR injection. The cardiologist must re-evaluate the ECG:

- If a QTcF > 470 msec is NOT confirmed, no further action needs to be taken.
- If a QTcF > 470 msec is confirmed, a cardiologist must perform a thorough examination (such as reviewing baseline ECG, concurrent medications and performing a cardiovascular examination, including at least a cardiac auscultation) to assess the patient for cardiovascular risk factors.
- If based upon the assessment by the cardiologist, the investigator considers that there is an acute cardiovascular safety risk and that the patient should not continue with study medication, the patient needs to be discontinued immediately (discontinuation criteria to be followed as described in [Section 7.1.3](#)).
 - If following the examination by the cardiologist, the investigator considers that there is no acute cardiovascular safety risk and that the patient could continue to receive study medication, a 24hr Holter ECG must be recorded at the next pasireotide LAR injection. The Holter-ECG must be started 30 min prior to an injection of study medication and a pre-dose PK sample will be taken.

If at any visit at trough level (28 days after the previous dose) a QTcF/mean QTcF > 470 msec but \leq 500msec is observed for the first time for a patient at a given dose level, the following steps need to be taken (please also refer to [Figure 6-2](#)):

[figure not shown]
A cardiology consultation must be sought as soon as practical but within 7 days of the initial abnormal ECG and prior to the next pasireotide LAR injection. The cardiologist must re-evaluate the ECG.

- If a QTcF > 470msec is NOT confirmed, no further action needs to be taken.
- If a QTcF > 470msec is confirmed, a cardiologist must perform a thorough examination (such as reviewing baseline ECG, concurrent medications and performing a cardiovascular examination, including at least a cardiac auscultation) to assess the patient for cardiovascular risk factors.
- If based upon the assessment by the cardiologist, the investigator considers that there is an acute cardiovascular safety risk and that the patient should not continue with study medication, the patient needs to be discontinued immediately (discontinuation criteria to be followed).

- If following the examination by the cardiologist, the investigator considers that there is not an acute cardiovascular safety risk and that the patient could continue to receive study medication, a 24hr Holter ECG must be recorded and evaluated prior to the next injection of pasireotide LAR and a trough PK sample will be taken. The pasireotide LAR injection must be postponed with a maximal permissible delay of 7 days until the Holter-ECG results are available. If the outcome of the cardiac evaluation is that the patient may receive a further dose of pasireotide LAR, then a second 24hr Holter-ECG must be done on the day of the injection and a pre-dose PK sample must be taken. This Holter ECG should be started 30min prior to the injection.

The results of the ECGs, cardiac examination, Holter-ECGs and the recommendation by the cardiologist must be evaluated by the investigator to determine whether the patient should continue in the study or not (discontinuation criteria to be followed as described in [Section 7.1.3](#)).

Figure 6-2 QT prolongation monitoring flow chart

6.3.3.3 Hepatic safety management

If any of the criteria below are observed at any scheduled or unscheduled visit the sponsor should be notified immediately upon awareness.

- ALT or AST > 3 x ULN and Total Bilirubin \geq 2 x ULN
- ALT or AST > 5 x ULN and \leq 8 x ULN
- ALT or AST > 8 x ULN

The following should be performed immediately within **72 hours** of awareness of the above abnormality:

- Perform liver-directed medical history and physical examination (i.e. assess occupational hazards, concomitant medications including OTC meds, inter-current illness, etc)
- Liver chemistry tests: ALT, AST, total bilirubin (fractionated to direct/indirect if total bilirubin is >2.0 x ULN), Alb, PT (INR), ALP, and GGT
- Perform hepatitis screen: anti-HAV, IgM (to confirm acute Hepatitis A), HBsAg, Anti-HBc, anti-HCV (if positive, PCR viral load should be assessed), Anti-HEV, ANA antibodies, anti-smooth muscle anti-bodies, CMV and EBV
- Perform abdominal ultrasound (liver and biliary tree)
- Collect PK sample and record the dose level and the dosing time for the last dose the patient has taken prior to PK sampling

Liver chemistry tests (LFTs) should be monitored every **3-4 days** until resolution or return to baseline status.

[figure not shown]
Patients or subjects may need to be discontinued if the abnormal liver function criteria are met upon LFT retesting (See criteria for premature withdrawal criteria [Section 7.1.3.1](#)). Progress reports of the event should be maintained until resolution or stabilization (i.e. no further elevation after 2 consecutive assessments).

For ALT or AST > 5 x ULN and \leq 8 x ULN, the following must occur (in addition to the safety follow up procedures noted above)

- Study medication should be temporarily interrupted and liver chemistry tests monitored every **3-4 days** until resolution or return to baseline.
- If resolution or return to baseline does not occur after 2 weeks, the patient should be discontinued.
- If ALT or AST (or both if ALT and AST were elevated) return to less than 5 x ULN study drug can be resumed and patient can continue study per protocol.
- If ALT or AST rises above 5 x ULN any time after study drug is resumed, then study drug should be discontinued immediately.

If any of these criteria are met and deemed an adverse event by the investigator, the event must be recorded on the Adverse Event (e) CRF page; if the event is deemed serious by the investigator, then proceed with completing the SAE form. In addition, any significant findings from the physical examination should be recorded on the Adverse Event (e) CRF page.

Figure 6-3 LFT management algorithm

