7.1.3.1 Criteria for premature patient withdrawal

Patients may voluntarily withdraw from the study or be dropped from it at the discretion of the investigator at any time. Patients may be withdrawn from the study if any of the following occur:

- Adverse event(s) [including abnormal laboratory value(s) and abnormal test procedure result(s)]
- Protocol deviation (including but not limited to, new therapy for acromegaly, and discovery of patient ineligibility)
- Patient withdrew consent

- Lost to follow-up
- Administrative problems
- Death
- Disease progression
- Pregnancy
- Treatment duration completed as per protocol

The investigator must also inform the premature withdrawal to Novartis, if this occurs during the core period.

In addition to the general withdrawal criteria, the following **study specific criteria** will also require study treatment discontinuation:

- Patients experiencing unacceptable toxicity, as described in [Table 6-2](#), [Table 6-3](#).
- Patients unable to tolerate the lowest dose (20 mg) as per [Section 6.3](#).
- Patients with > 28 consecutive days of treatment interruption (either due to tolerability, investigator decision or patient compliance)
- Uncontrolled diabetes mellitus, consistently high glucose values FPG \geq 240 mg/dL (13.3 mmol/L) or HbA1c value \geq 10 % despite prior appropriate management and prior dose adjustment of the study drug,
- Patients experiencing adverse events in QTc:
 - a confirmed QTcF $>$ 470msec and discontinuation recommended by a cardiologist, or
 - Mean QTcF $>$ 500 msec measured by triplicate ECGs
 - Significant arrhythmia findings from Holter monitoring such as:
 1. Any ventricular or supra-ventricular tachyarrhythmia associated with symptoms of hemodynamic compromise
 2. Sustained ventricular tachycardia ($>$ 30 sec) irrespective of symptoms
 3. Recurrent non-sustained ventricular tachycardia (\geq 3 beats) during any 24-hour monitoring period
 4. Torsades de Pointes
 5. Cardiac arrest
 6. Pause $>$ 5 seconds
 7. Second or third degree AV block
 - New occurrence of clinically significant/symptomatic bradycardia, or
 - Increased risk of QT prolongation by use of QT prolonging medication, or
 - Hypokalemia ($<$ 3.5 mmol/L) or hypomagnesaemia ($<$ 0.7 mmol/L) confirmed by repeat testing that is either a new finding or accompanied by vomiting or diarrhea and not corrected by treatment.
- Patients experiencing the abnormal hepatic criteria below:

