 - ALT or AST $>$ 3 x ULN and Total Bilirubin \geq 2 x ULN and ALP $<$ 2 x ULN
 - ALT or AST $>$ 5 x ULN and \leq 8 x ULN persistent for more than 2 weeks

- ALT or AST > 8 x ULN
- Lack of efficacy: during the core phase treatment period, patients with GH level > 2.5ug/L and/or IGF-1 > ULN (age and sex related) be discontinued from the study unless clinical benefit has been observed as per the investigator's judgment.

Patients who withdraw prematurely from the core phase cannot participate in the extension phase.

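### For two hepatic criteria, protocol 7.1.3.1 requires treatment to stop and states no retest, while 6.3.3.3 says stopping may follow if the criteria are met on retest

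*Protocol*

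**What the plan says.** Protocol 6.3.3.3 lists three liver findings that must be notified to the sponsor at once: ALT or AST above 3 x ULN with total bilirubin at least 2 x ULN; ALT or AST above 5 and up to 8 x ULN; and ALT or AST above 8 x ULN. Each leads to a work-up that includes repeat liver chemistry within 72 hours, and then to monitoring every 3–4 days. On stopping, the section says: "Patients or subjects may need to be discontinued if the abnormal liver function criteria are met upon LFT retesting". It then points to 7.1.3.1.

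The text of 6.3.3.3 gives step-by-step instructions only for the middle band. There, "Study medication should be temporarily interrupted and liver chemistry tests monitored every" 3–4 days; "If resolution or return to baseline does not occur after 2 weeks, the patient should be discontinued"; and if ALT or AST "rises above 5 x ULN any time after study drug is resumed, then study drug should be discontinued immediately".

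Protocol 7.1.3.1 introduces its study-specific criteria as ones that "will also require study treatment discontinuation". The hepatic entry opens with "Patients experiencing the abnormal hepatic criteria below" and has three lines:

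- ALT or AST above 3 x ULN with total bilirubin at least 2 x ULN and ALP below 2 x ULN
- the middle band, but only if "persistent for more than 2 weeks"
- "ALT or AST > 8 x ULN", with nothing added

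**The concern.** The two sections deal with the same laboratory findings but differ in force (*may need to* against *will require*) and in trigger (on retest against no retest stated). The difference falls on the highest transaminase level and on the combined transaminase–bilirubin pattern.

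What is at stake is whether the next 28-day depot injection is given. It also affects how the case is recorded. Protocol Section 12 permits no authorised deviations, so conduct that follows one section could be classed as a deviation from the other. A discontinuation enters the SAP disposition and adverse-event tables. If it comes before the Month 3 assessment, protocol 10.4.3 and SAP 4.1.9 count the patient as a non-responder. SAP 5.10.2.1 counts potential Hy's Law events from a single sample with no retest, so a patient could be tabulated there and still have continued treatment under 6.3.3.3.

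**Working it through.** The plan gives no figure on this point to reproduce. The check is a comparison by criterion, followed by a bound on the effect.

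**Comparison by criterion**

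| Finding | 6.3.3.3 | 7.1.3.1 | Same rule? |
|---|---|---|---|
| ALT/AST > 8 x ULN | may need to stop, if met on retest | stop required, no retest stated | No: force and trigger differ |
| ALT/AST > 3 x ULN, bilirubin ≥ 2 x ULN, ALP < 2 x ULN | as above, with no ALP condition | stop required, no retest stated | No: force and trigger differ |
| ALT/AST > 3 x ULN, bilirubin ≥ 2 x ULN, ALP ≥ 2 x ULN | may need to stop, if met on retest | combined criterion does not apply | ALP condition is in one section only |
| ALT/AST > 5 to 8 x ULN | interrupt; stop if not resolved or at baseline after 2 weeks | stop if persistent for more than 2 weeks | Broadly yes |

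**Does the cross-reference settle it?** The 7.1.3.1 list writes out confirmation or persistence elsewhere: repeat testing for low potassium or magnesium, confirmation for QTcF above 470 msec, triplicate ECGs for mean QTcF above 500 msec, and more than two weeks for the middle liver band. Two hepatic lines have no such words. Reading the 6.3.3.3 retest into them is possible, but nothing in 7.1.3.1 says so. Even if it is read in, *may* against *will require* remains.

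**A path on which the sections part.** Take ALT above 8 x ULN once. On retest ALT and AST are at or below 5 x ULN and bilirubin is below 2 x ULN, so no 6.3.3.3 criterion is met. Under 7.1.3.1 the patient has experienced a listed criterion and stopping is required. Under 6.3.3.3 the condition for considering a stop is not met, and the text gives no other stopping or interruption instruction for this patient.

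**Size.** One patient reclassified moves a proportion by 1/n:

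- n = 33 (randomised): 1/33 = 3.0 points
- n = 30 (planned): 1/30 = 3.3 points

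For the primary endpoint, the lower limit of the Clopper-Pearson two-sided 90% interval with r responders is the 5th percentile of Beta(r, n − r + 1). The plan's minimum meaningful rate is 10%.

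| n | r = 6 | r = 7 |
|---|---|---|
| 30 | 9.1% | 11.5% |
| 33 | 8.2% | 10.4% |

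One patient changes the comparison with 10% only at the step between 6 and 7 responders. The patient must also be one who would otherwise have responded.

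**The case against.** The best reply is that 6.3.3.3 defers to 7.1.3.1. On that reading it is a pointer to the operative list, and *may* is accurate because not every alert is a stopping criterion: the bilirubin alert becomes one only with low ALP, and the middle band only if it persists. This explains the softer verb for those findings. It does not explain it for ALT or AST above 8 x ULN, which appears in both lists without qualification, and it does not explain the retest wording.

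Second, Figure 6-3 is the protocol's liver algorithm and may set out the sequence. It is not visible in the text reviewed, so this stands as a limit on certainty. It would not by itself make the two written sections agree.

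Third, the sponsor must be told of every such value at once, which makes unnoticed divergence between sites less likely. That is fair, but the sponsor would then be advising from two texts that differ.

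Several stronger readings are tempting, and the documents do not support them:

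- *6.3.3.3 stops a patient only on a repeat value, and 7.1.3.1 on the first.* Neither expression is in the text. The first-value reading is inferred from silence, and 6.3.3.3 itself orders an immediate stop, with no retest mentioned, for a rise above 5 x ULN after resumption.
- *The conflict covers any raised ALT or AST.* It does not reach the middle band.
- *A fall from 9 to 6 x ULN moves the patient into the band where treatment may resume.* At 6 x ULN a 6.3.3.3 criterion is still met on retest, and nothing says that a patient first seen above 8 x ULN is reclassified.
- *A stopped patient is a stated non-responder at every later core visit.* The explicit rule covers Month 3. For later core visits, SAP 4.1.10 says only that discontinued patients stay in the denominator.

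**Conclusion.** The point holds for two of the three hepatic criteria in 7.1.3.1. For these the protocol gives two rules that differ in force and trigger, and the ALP condition appears in only one section. The same result could lead to stopping under one section and continuation under the other when the retest meets none of the 6.3.3.3 criteria.

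The main consequence is for treatment decisions and for how cases are classified. The effect on results is small: at most 3.0 points per affected patient with n = 33, through the Month 3 non-responder rule or the core-phase denominator. The number of such patients is not given. Enrolment is complete, and SAP 5.9.1 says that the primary result has been reported, so what remains is any continuing treatment and consistent classification in the final report. The conclusion rests on the written sections alone, because Figure 6-3 could not be read. It should be corrected, but it does not undermine the primary analysis.

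**What to change.** Reconcile protocol 6.3.3.3 with 7.1.3.1 and check both against Figure 6-3. For ALT or AST above 8 x ULN, and for the combined transaminase–bilirubin criterion, both sections should state the same:

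- trigger, with or without a retest
- force, *may* or *will require*
- ALP condition

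Which rule is right is a clinical decision for the sponsor, and none is proposed here.

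The cost is a few words in an amendment, with the approvals that Section 12.1 calls for. No new procedure or data are needed, because the retest is already required. If no patient remains on treatment, the final report can instead state which reading was applied and list any patient who met either criterion, with the retest result and the treatment decision.

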13. Patients with risk factors for torsade de pointes, i.e. patients with a baseline QTcF > 470 ms, hypokalemia, hypomagnesemia, hypocalcemia, family history of long QT syndrome, or patients receiving a concomitant medication known to prolong QT interval.
14. Patients with confirmed central hypothyroidism, central hypoadrenalism and diabetes insipidus, unless they are adequately treated with stable doses of hormone replacement therapy for a minimum of three months prior to study entry (first dose of study medication). Patients with confirmed central hypogonadism unless they are adequately treated with stable doses of hormone replacement therapy for a minimum of three months prior to study entry (first dose of study medication) except in cases where hormones replacement therapy is not indicated.
15. Patients with history of liver disease such as cirrhosis, chronic active hepatitis B or C, or patients with ALT or AST more than 2 x ULN, baseline total bilirubin > 1.5 x ULN
16. Presence of Hepatitis B surface antigen (HbsAg)
17. Presence of Hepatitis C antibody (anti-HCV)
18. Patients with WBC <3 x 10⁹/L; Hgb < 90 % LLN; PLT <100 x 10⁹/L
19. Patients who have any current or prior medical condition that may interfere with the conduct of the study or the evaluation of its results in the opinion of the Investigator
20. Female patients who are pregnant or lactating, or are of childbearing potential (defined as all women physiologically capable of becoming pregnant) and not practicing an effective method of contraception/birth control. Female patients of child bearing potential and sexually active males must use a condom during intercourse while taking the drug and for 3 months after the last dose of study drug and should not father a child in this period. A condom is required to be used also by vasectomized men in order to prevent delivery of the drug via seminal fluid. Effective contraception methods include:
 - Use of oral, injected or implanted hormonal methods of contraception
 - Placement of an intrauterine device or intrauterine system
 - Barrier methods of contraception: condom or occlusive cap (diaphragm or cervical/vault caps) with spermicidal foam/gel/film/cream/ vaginal suppository
 - Total abstinence
 - Patient sterilization (male or female)
21. Patients who have a history of alcohol or drug abuse in the 12 month period prior to receiving pasireotide LAR

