10.4.3 Handling of missing values/censoring/discontinuations

If the GH and/or IGF-1 samples are taken after 35 days from the date of any LAR injection, the values of GH and/or IGF-1 at the corresponding visit will be treated as missing. In addition, if a patient has less than 3 samples for the assessment of 5-point mean GH levels from the 2-hour profile, the mean GH levels will be considered as missing.

The patients with missing values of mean GH levels and/or IGF-1 at 3 months of study treatment or who discontinue prior to the assessment at 3 months of study treatment will be considered as non-responders.

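### For ALT/AST above 5 and up to 8 x ULN, the stop and resume instructions overlap for patients who have only partly recovered at 2 weeks

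*Protocol*

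**What the plan says.** Protocol 6.3.3.3 gives four bullets for ALT or AST above 5 and up to 8 x ULN, introduced as actions that must occur:

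- First: "Study medication should be temporarily interrupted and liver chemistry tests monitored every" 3 to 4 days, until resolution or return to baseline.
- Second: "If resolution or return to baseline does not occur after 2 weeks, the patient should be discontinued".
- Third: if the raised enzyme or enzymes "return to less than 5 x ULN study drug can be resumed and patient can continue study per protocol".
- Fourth: "If ALT or AST rises above 5 x ULN any time after study drug is resumed, then study drug should be discontinued immediately".

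Protocol 7.1.3.1, to which 6.3.3.3 refers for withdrawal criteria, lists conditions that require study treatment to be discontinued. For this range the condition is ALT or AST above 5 and up to "8 x ULN persistent for more than 2 weeks".

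Two other provisions bear on the point. Exclusion criterion 15 in Protocol 5.3 keeps out "patients with ALT or AST more than 2 x ULN", so a return to baseline means a return to 2 x ULN at most. Protocol 10.4.3 provides that patients "who discontinue prior to the assessment at 3 months of study treatment will be considered as non-responders".

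**The concern.** The second and third bullets use different yardsticks. The second asks whether the value has resolved or returned to baseline by 2 weeks. The third asks only whether it is below 5 x ULN. Neither says which prevails, and *resolution* is not defined. The criterion in 7.1.3.1 uses a third form, persistence within the range. A patient who has clearly improved but has not recovered fully can fall under both bullets of 6.3.3.3 and outside 7.1.3.1.

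This is a safety stopping rule. If two sites read it differently, one patient is re-exposed and a similar patient is withdrawn, both with support in the text. Withdrawals for liver enzymes would then partly reflect how each site read the rule. A withdrawal before the 3-month assessment is also scored as a non-response in the primary analysis.

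**Working it through.** The plan gives no figure to reproduce here, so the check applies the three conditions to the same 2-week value.

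**Inputs**
- Stop condition S (6.3.3.3, second bullet): not resolved and not back to baseline after 2 weeks.
- Restart condition R (6.3.3.3, third bullet): value below 5 x ULN.
- Withdrawal condition W (7.1.3.1): value still above 5 and up to 8 x ULN for more than 2 weeks.
- Baseline: at most 2 x ULN (5.3, criterion 15).
- Assumption: *resolution* means at or below ULN. The text does not say this.

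**Result under that assumption, just past 2 weeks**

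| Value (x ULN) | S: stop | R: may restart | W: stop |
|---|---|---|---|
| At or below ULN, or at or below baseline | no | yes | no |
| Above both ULN and baseline, below 5 | **yes** | **yes** | no |
| Exactly 5.0 | yes | no | no |
| Above 5, up to 8 | yes | no | yes |

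The overlap is the second row. For a baseline at or below 1 x ULN it runs from above 1 to below 5 x ULN. For the highest baseline allowed, 2 x ULN, it runs from above 2 to below 5 x ULN. A patient who peaks at 6 and is at 3 x ULN at 2 weeks is in the overlap whatever the baseline. So is a patient restarted at 4 x ULN before 2 weeks who is still above both ULN and baseline at 2 weeks.

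**Result if resolution means below 5 x ULN**

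S then applies at 5 x ULN and above, R applies below 5, and W applies above 5. The three agree except at exactly 5.0 x ULN, where S stops and W does not. The conflict therefore depends on the undefined word.

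**Link to the primary endpoint**

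With 33 patients randomized, one patient is 1/33 = 3.0 percentage points of the response rate. A stop before Month 3 lowers the rate by that amount only if the patient would otherwise have responded. At the 30% response rate used for planning in Protocol 10.8, and assuming it applies to these patients, the average loss per stop is 0.30 x 3.0 = 0.9 points. The Clopper-Pearson 90% lower limit is 8.2% for 6/33 and 10.4% for 7/33, so one responder could decide whether the limit reaches the 10% planning value. That arithmetic is not tied to any hepatic event: the documents give no rate for this elevation.

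**The case against.** The strongest reply is that the bullets are coherent if *resolution* means that the triggering abnormality has cleared, that is, the value is below 5 x ULN. This reading is possible, and 7.1.3.1 fits it. The text does not state it, however, and pairs the word with return to baseline. Since baseline is at most 2 x ULN, any patient back at baseline is already below 5 x ULN, so on this reading the baseline alternative would add nothing.

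A second reply is that 7.1.3.1 controls, because 6.3.3.3 refers to it. It does not require a stop at 3 x ULN, which would leave the second bullet as the outlier. But no order of precedence is given, and the second bullet is itself written as a discontinuation instruction.

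Third, the wording is asymmetric: drug *can* be resumed, while the patient *should* be discontinued. A site that stops breaches neither bullet. This stands and softens the conflict. It does not remove it, because a site that restarts relies on an express permission.

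Fourth, Figure 6-3, the LFT management algorithm, may settle the matter. The footnote to Table 6-2 sends sites to it, and its content is not in the text available to us. This limits the certainty of the point. Even a clear figure would leave 6.3.3.3 and 7.1.3.1 worded differently.

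**Conclusion.** The point holds as an inconsistency in the protocol text, confined to a defined group: patients who entered the range above 5 and up to 8 x ULN and who, at 2 weeks, are below 5 x ULN but above both ULN and their own baseline. It rests on *resolution* not meaning below 5 x ULN, and it is subject to Figure 6-3. It merits correction because it concerns a liver safety stop.

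Three stronger readings are tempting, and the documents do not support them:

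- A reader might infer that every value between baseline and 5 x ULN is in conflict. It is not. A patient with baseline 0.8 who is at 0.9 x ULN is within normal limits and has resolved on any ordinary reading.
- A reader might infer that the rule gives flatly opposite orders and cannot be applied. One side is only a permission, a reconciling reading exists, and the algorithm figure has not been seen.
- A reader might infer that the primary result is at risk. The frequency is unknown, a stop changes the rate only for a would-be responder, and 10% is a planning value: Protocol 10.4.2 specifies an estimate with a confidence interval and states no test against it.

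**What to change.** Define *resolution* in 6.3.3.3, and reconcile the second and third bullets, the 7.1.3.1 criterion and Figure 6-3 so that a single stop/resume condition applies, including at exactly 5 x ULN. Which condition to adopt is for the sponsor's hepatic safety team; this review takes no position. The cost is wording in an amendment or an investigator letter, with no new procedures. It matters for any patient still on treatment, since liver tests continue in the extension schedule (Table 7-2).

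Enrollment is complete, and the Month 3 and Month 12 analyses have been done (SAP 1 and 4.2). For those results the proportionate step is to check whether any patient met the overlap and, if so, to report what was done and whether it fell before the 3-month assessment. SAP 5.10.2.1 already counts patients with a worst post-baseline ALT or AST above 5 x ULN. That count is an upper bound on how many patients could have been affected; if it is zero, the point has no consequence for the reported data.
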